#### **Night splints**

The primary outcome measure here is the measured angle of the knee or ankle (in the sagittal plane) in degrees [2, 4]. A secondary outcome measure is patient satisfaction, measured using the OPUS/CSD scale, which questions the patient's satisfaction with the orthosis, and the range of motion (ROM) of the ankle or knee in degrees.

Only new patients are recruited for this target group, as there is a therapeutic effect of the orthosis that was worn.

The patients will be fitted with both a new traditional orthosis and a new 3D printed orthosis. The study is designed so that all patients are fitted with both types of orthosis in a crossover design.

The two pathologies that are included and for which patients are recruited, also give rise to two different types of orthosis: an ankle-foot orthosis (AFO) for patients with foot stance disorders, and a knee-ankle-foot orthosis (KAFO) for patients with genu varum.

The patients are only measured without wearing the orthosis (2 times each time). The first baseline measurement is taken at the start of the measurement campaign (T0). For each type of orthosis, the patient is given 3 weeks to wear the orthosis before being checked for a new measurement. After the first phase with the first orthosis (traditional or 3D printed), the patient is measured again (T1) without the orthosis. After the second stage with the second orthosis (3D printed or traditional), the patient is measured again (T2) without the orthosis.

#### Sample size

Here, the primary outcome measure is the measured angle of the ankle or knee. A secondary outcome measure here is patient satisfaction, calculated from the OPUS-CSD scale and measured ROM. Our sample size is not adjusted for multiple testing.

The calculation of the sample size is similar to that of the first patient group. However, there are now 3 moments where we will compare the angles (T0, T1, T2), and a lower value for the correlation is expected, since an influence of the treatment is expected, and the correlation at successive measurements may be smaller. The correlation is estimated here at 0.4. This gives a patient number of 12 per group (48 in total).

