#### Sample size

As indicated above, the primary outcome measure is the measured speed during the 10m walk test. A secondary outcome measure here is patient satisfaction, calculated from the OPUS-CSD scale. Our sample size is not adjusted for multiple testing.

The sample size was calculated based on an effect size estimate of 25%, and an  $\alpha$  equal to 5%, and a power of 80% ( $\beta$  = 0.20). In total, there are 4 groups (2 between-subject factors with 2 levels each), and we compare at 2 measurement points, T1 and T2. We expect that measured patient parameters (the speed) do not change that much over time and with the orthosis, so we take a correlation of 0.6.

This gives a total of 40 patients, or 10 patients per group. With a margin of 20% for drop-out, we arrive at 12 patients per group (total of 48).

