#### 4. PATIENT SELECTION

The recruitment of the maximum of 105 subjects will be done on the one hand by contacting patients who are already in the contact details of the orthopaedic centres involved, and this specifically for patients who will be fitted with the dynamic orthoses. On the other hand, the patients receiving the night splint will be new patients.

Patients and parents of patients in this second target group will be given information about the research project by means of a visual information sheet when they check in at the centre. The doctor or staff member will inform the patient and parents in detail about the research project. They can then decide whether or not to take part in the study.

The patients from the first target group will be contacted by a staff member of the centre who will explain the research project. The patient has the time to make a voluntary decision whether or not to take part in the research project. If the patient is interested in participating, he/she is invited to come to the centre, where the visual information sheet will explain the project once more. The information and consent form will be presented for signing before entering the project.

Patient selection Patients with foot stance deformities - Inclusion o Age: >= 2 years, <= 6 years Gender: any gender Pathology: foot stance deformity o Unilateral as well as bilateral orthoses were included - Exclusion o Patient is already wearing a night splint Patients with genu varum - Inclusion Age: >= 2 years, <= 6 years Gender: any gender Pathology: genu varum o Both unilateral and bilateral orthoses are included - Exclusion o Patient is already wearing a night splint o The patient cannot stand upright

Patients with drop foot

- Inclusion

Age: >= 18 years

Gender: any gender Pathology: drop foot Patient is already wearing foot orthosis for drop foot Patient is able to walk at least 10 meters with or without the assistance of an aid (such as a cane) - Exclusion Wearing bilateral orthosis Wearing other orthosis (such as corset) Having a mental disorder The patient is pregnant Patients with knee instability - Inclusion o Age: >= 18 years Gender: any Pathology: knee instability Patient is already wearing an orthosis for knee instability Patient is able to walk at least 10 meters with or without the aid of an aid (such as a cane) - Exclusion Wearing a bilateral orthosis Having a mental disorder, neurological disorder o The patient is pregnant

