All subjects may decide to withdraw from the study at any time without giving a reason.

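### The night-splint total of 48 carries no drop-out margin, unlike the dynamic-orthosis 48; at the protocol's own drop-out allowance its power is about 69–72%, not 80%

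*Protocol*

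**What the plan says.** In the Protocol's Sample size section for dynamic orthoses, the calculation has two steps. The inputs are an effect size ("The sample size was calculated based on an effect size estimate of 25"%), an alpha "equal to 5%, and a power of 80"%, four groups, two measurement points and a correlation of 0.6. The result before drop-out is "This gives a total of 40 patients, or 10 patients per group". The margin is then added: "With a margin of 20% for drop-out, we arrive at 12 patients per group (total of 48").

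The Sample size section for night splints has one step. It says "The calculation of the sample size is similar to that of the first patient group", changes the number of measurement points to three and the correlation to 0.4, and concludes "This gives a patient number of 12 per group (48 in total"). It mentions no drop-out, and it does not restate the effect size, alpha, power or number of groups.

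Section 4 (Patient selection) caps the trial ("The recruitment of the maximum of 105 subjects") and states that "All subjects may decide to withdraw from the study at any time without giving a reason".

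**The concern.** The two cohorts end on the same total, 12 per group and 48 overall, so a reader will assume that both are equally protected against loss. The text suggests otherwise: one 48 comes after a drop-out step and the other has no such step. The night-splint wording also matches the wording used for the dynamic figure before drop-out.

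If the night-splint 48 is the bare requirement, any material loss takes that cohort below the 80% power carried over from the dynamic section. This affects its primary outcome, the joint angle, and a null result could be read as coming from an 80%-power comparison when it did not. Drop-out cannot be dismissed: subjects may withdraw freely, and both cohorts pass through the same two 3-week periods for which the dynamic section allows 20%.

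**Working it through.** **Inputs from the Protocol.** Effect size 25%, alpha 0.05, power 0.80 and k = 4 groups come from the dynamic Sample size section. Dynamic orthoses have m = 2 time points and correlation ρ = 0.6. Night splints have m = 3 and ρ = 0.4.

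**Assumptions.** 25% means Cohen's f = 0.25. The night-splint calculation reuses the effect size, alpha, power and four groups. The test is the groups-by-time (within-between) interaction of a repeated measures ANOVA under sphericity.

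**Formula.** The test statistic is noncentral F with
- λ = f² · N · m / (1 − ρ)
- df1 = (k − 1)(m − 1)
- df2 = (N − k)(m − 1)

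**Step 1: reproduce the dynamic figure.**
- N = 36: λ = 0.0625 × 36 × 2 / 0.4 = 11.25, df 3 and 32, power 75.9%.
- N = 40: λ = 0.0625 × 40 × 2 / 0.4 = 12.5, df 3 and 36, power 81.2%.

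The smallest total in equal groups is 40, the protocol's figure before drop-out. Then 40 × 1.2 = 48, as stated.

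**Step 2: apply the same method to night splints.**

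| Completers N | λ = 0.0625 × N × 3 / 0.6 | df1, df2 | Power |
|---|---|---|---|
| 48 | 15.0 | 6, 88 | 81.2% |
| 47 | 14.69 | 6, 86 | 80.1% |
| 46 | 14.375 | 6, 84 | 79.0% |
| 44 | 13.75 | 6, 80 | 76.7% |
| 40 | 12.5 | 6, 72 | 71.5% |
| 38 | 11.875 | 6, 68 | 68.6% |

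The smallest total in equal groups is 48, the stated figure, with nothing left for drop-out. The second drop-out takes power below 80%. Reading 48 as 40 plus 20% fails, because 40 completers give only 71.5%.

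**Step 3: check whether another test explains the figures.** Smallest totals in equal groups for 80% power:

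| Test | Dynamic | Night splints |
|---|---|---|
| Interaction, 4 groups | 40 | 48 |
| Within main effect, 4 groups | 28 | 36 |
| Between main effect, 4 groups | 144 | 112 |
| Interaction, 2 groups | 28 | 34 |
| Between main effect, 2 groups | 104 | 78 |

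Of these, only the four-group interaction gives both protocol figures. The within main effect would leave room for a margin in the night-splint 48 (36 / 0.8 = 45, rounded up to 48 in equal groups), but it does not give 40 for dynamic orthoses.

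**Step 4: apply the dynamic cohort's drop-out allowance.**
- Same ratio as the dynamic cohort: 48 / 1.2 = 40 completers (16.7% loss), power 71.5%.
- Full 20% loss: 48 × 0.8 = 38.4, about 38 completers, power 68.6%.
- Type II error: 28.5% to 31.4%, against 20% planned.
- Effect detectable with 80% power: f = 0.272 (N = 40) or 0.280 (N = 38), against 0.247 at N = 48.

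**Step 5: compare a matching margin with the cap.** 48 × 1.2 = 57.6, so 58; or 48 / 0.8 = 60. Adding the 48 dynamic patients gives 106 or 108, above the maximum of 105.

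**The case against.** Four points can be made on the other side.

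- **Unused places.** The two cohorts total 96 and the cap is 105, which leaves nine places. If all nine went to night splints, 57 could be enrolled. At the 48-to-40 loss rate that leaves about 47.5 completers (47 give 80.1%); at a full 20% loss it leaves about 45 to 46 (77.9% to 79.0%). This is true and worth stating. But the protocol assigns these places to no cohort, and its night-splint figure remains 48.
- **The test.** The four-group interaction has 6 numerator degrees of freedom and pools sequence, pathology and their combination. The contrast of traditional with 3D-printed orthoses lies in sequence by time, a two-group interaction. At f = 0.25 that has 86.5% power with 38 completers and 88.4% with 40. So 69–72% is the power of the test that the sample size appears to rest on, not necessarily of the treatment contrast. That limit on interpretation stands. It does not rescue the calculation, because the two-group test gives 28 and 34 rather than 40 and 48.
- **Transfer of the allowance.** The 20% was set for adults who already wear an orthosis, whereas the night-splint patients are newly recruited children aged 2 to 6. Their drop-out may differ, so the power figures are conditional. The protocol gives no reason to expect no loss.
- **No sum is wrong.** With 48 completers the stated calculation holds. That is correct; the fault is that a completer requirement is presented as the patient number beside a total that already includes a margin.

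**Conclusion.** The point holds. The dynamic 48 includes a 20% drop-out margin. The night-splint 48 states none and, on the only test tried that reproduces both protocol figures, contains none. With 48 enrolled and the drop-out allowance of the dynamic section, the night-splint cohort has about 69–72% power instead of 80%.

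This range rests on f = 0.25, the carried-over inputs, the four-group interaction, sphericity, and drop-outs contributing no data. Sphericity is the favourable case: with a sphericity coefficient of 0.75, power at 38 to 40 completers falls to about 59–62%. That the text applies a margin in one cohort and omits it in the one it calls similar does not depend on any of these assumptions. The point should be fixed.

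**What to change.** Reword the night-splint Sample size section to say that:

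- 48 is the number of completers needed, before any drop-out;
- the effect size (f = 0.25, if that is what 25% means), alpha, power and four groups are carried over from the dynamic section, and the test is the four-group by time interaction;
- at the drop-out allowed for in the dynamic section (38 to 40 completers), power for that test is about 69–72%.

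The section should also say what the nine places between 96 and the maximum of 105 are for, since they bear on whether any reserve exists.

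The cost is a few sentences of text, with no added patients, visits or measurements. No increase in enrolment is proposed, because a full matching margin would exceed the protocol's own cap.

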#### 4. PATIENT SELECTION

The recruitment of the maximum of 105 subjects will be done on the one hand by contacting patients who are already in the contact details of the orthopaedic centres involved, and this specifically for patients who will be fitted with the dynamic orthoses. On the other hand, the patients receiving the night splint will be new patients.

Patients and parents of patients in this second target group will be given information about the research project by means of a visual information sheet when they check in at the centre. The doctor or staff member will inform the patient and parents in detail about the research project. They can then decide whether or not to take part in the study.

The patients from the first target group will be contacted by a staff member of the centre who will explain the research project. The patient has the time to make a voluntary decision whether or not to take part in the research project. If the patient is interested in participating, he/she is invited to come to the centre, where the visual information sheet will explain the project once more. The information and consent form will be presented for signing before entering the project.

Patient selection Patients with foot stance deformities - Inclusion o Age: >= 2 years, <= 6 years Gender: any gender Pathology: foot stance deformity o Unilateral as well as bilateral orthoses were included - Exclusion o Patient is already wearing a night splint Patients with genu varum - Inclusion Age: >= 2 years, <= 6 years Gender: any gender Pathology: genu varum o Both unilateral and bilateral orthoses are included - Exclusion o Patient is already wearing a night splint o The patient cannot stand upright

Patients with drop foot

- Inclusion

Age: >= 18 years

Gender: any gender Pathology: drop foot Patient is already wearing foot orthosis for drop foot Patient is able to walk at least 10 meters with or without the assistance of an aid (such as a cane) - Exclusion Wearing bilateral orthosis Wearing other orthosis (such as corset) Having a mental disorder The patient is pregnant Patients with knee instability - Inclusion o Age: >= 18 years Gender: any Pathology: knee instability Patient is already wearing an orthosis for knee instability Patient is able to walk at least 10 meters with or without the aid of an aid (such as a cane) - Exclusion Wearing a bilateral orthosis Having a mental disorder, neurological disorder o The patient is pregnant

All subjects may decide to withdraw from the study at any time without giving a reason.

#### 5. EVALUATION OF SECURITY

Previous studies [1, 7] have shown that there are no particular risks associated with wearing orthoses that are 3D printed as a whole, or with parts that are 3D printed. In particular, in this study the customised parts will be printed, while the parts that will be subjected to the greatest mechanical stress (such as the hinges and straps) are standard orthopaedic parts. This makes the risks as high as with traditionally designed orthoses. Subjects will not be exposed to unacceptable risks.

#### 6. DATAMANAGEMENT

The data entered in the local orthopaedic centres remain on site in the patients' medical files, as is done in the regular course of business, and are only accessible to the doctors on site.

The encrypted patient data are digitally entered into a platform that is specifically used for conducting patient surveys, is shielded and only accessible to the researchers working on this project. At the latest 2 years after the end of the project, the data will remain accessible only to the local orthopaedic centres, as the patient data are included in the patient files there.

